23. BIOLOGICAL MATERIALS TRANSFER AGREEMENT

A materials transfer agreement is on file with UCSD.

24. INVESTIGATIONAL DRUG FACT SHEET:

See Attached – Package Insert for Keppra

25. IMPACT ON STAFF:

Neonatal residents, fellows and attendings will be asked to identify patients at risk, briefly discuss the study with patients families and request permission to notify study staff.

Respiratory technicians and nurses or EEG technicians together with study investigators will be required to apply continuous EEG monitors, depending on the procedures in place at each study site.

If blood collection is to be done via indwelling catheters, the infant's primary nurse will be required to draw these labs.

Nursing staff will be asked to administer the IV medication.

Investigational pharmacy will prepare all doses of medication.

Study staff will conduct all other duties, including the labeling and sending of specimens for collection.

The procedures to be done by non-study staff require minimal additional time and are not expected to adversely impact the staff.

26. CONFLICT OF INTEREST (COI)

None

27. SUPPLEMENTAL INSTRUCTIONS FOR CANCER-RELATED STUDIES

NA

28. PROCEDURES FOR SURROGATE CONSENT AND/OR DECISIONAL CAPACITY ASSESSMENT

NA

29. HIPAA AND CONFIDENTIALITY

Application for partial waiver of HIPAA authorization is requested for the recruitment process in order to allow communication between clinicians and investigators. Specifically the waiver of consent for the transfer from the clinical team to the study team of clinical information needed to determine patient eligibility for the study is required. This was granted in our currently active IRB levetiracetam protocol.

Protected health information will be entered into the database with the consent of the subject's parents. In addition to the pharmacokinetic, seizure cessation and safety data for each patient, data entered will include demographic data and clinical baseline data, such as gestational age, mode of delivery, postnatal age at presentation, presumed etiology but personal identifiers such as name, date of birth and medical record

number will be eliminated from each case as it is entered in the database Personally identifiable data will not be publicly disclosed. Single copy of list linking medical record number to study number will be kept locked and available only to study investigators. Data will be entered on single secure database, accessible only by study investigators.

Study records will not be released without separate consent, except as required by law.
Code linking medical record to study number in the database will be destroyed once the study is published.

## 1 Introduction

This document is the second version of the Statistical Analysis Plan (SAP) describing the planned analyses and reporting for the NEOLEV2 trial. The SAP was updated due to a change in primary outcome from seizure termination at 48 hours after treatment to seizure termination at 24 hours after treatment. This change was approved by the FDA on September 4, 2018.

The planned analyses identified in this SAP, will be included in future manuscripts. Exploratory analyses not necessarily identified in this SAP may be performed to support planned analyses. Any post-hoc or unplanned analyses not specified in this SAP will be clearly identified as such in the manuscripts for publication.

The following documents were reviewed when preparing this SAP:

- NEOLEV2 Clinical Research Plan (*111361 NEOLEV2 Research Plan Clean 20180413.docx*)
- ATRI Statistical Analysis Plan SOP

Readers of this SAP should read the Clinical Research Plan for details on the conduct of this study and the operational aspects of clinical assessments and timing for completing a patient in this study.

## 2 Abbreviations

ABBREVIATION	DEFINITION
AE	Adverse Event
ATRI	Alzheimer's Therapeutic Research Institute
CRF	Case Report Form
DSMC	Data and Safety Monitoring Committee
LEV	Levetiracetam
PB	Phenobarbital
PK	Pharmacokinetic
PP	Per-Protocol
SAE	Serious Adverse Event
SAP	Statistical Analysis Plan
SOP	Standard Operating Procedure

## 3 Study Design/Summary

### 3.1 Overview

*This section is from the NEOLEV2 Clinical Research Plan (111361 NEOLEV2 Research Plan Clean 20180413.docx).*

This study will be a phase II preliminary efficacy, dose escalation and safety study. The study design will be a randomized blinded controlled treatment study. Infants recognized as having neonatal seizures or as being at risk of developing seizures will be recruited and started on continuous video EEG monitoring. The EEG data will then be reviewed continuously for electrographic seizures by study investigators, along with remote continuous EEG monitoring by Corticare technicians. A novel seizure detection algorithm operating in near-real time will be compared to the real-time continuous EEG reading. Once eligibility and consent are confirmed, patients will be randomly assigned to the LEV or control treatment group in a 60:40 allocation ratio, stratified by site.

Blinding will be maintained by appropriate dilution of LEV and Phenobarbital such that the same volume (ml/kg) loads are given to both treatment groups.

Subjects randomized to receive LEV will, at the onset of electrographically confirmed seizure activity, receive an intravenous loading dose of LEV of 40mg/kg given over 15 minutes. If electrographic seizures are confirmed to persist or recur more than

CONFIDENTIALITY STATEMENT: This report from the USC Alzheimer's Therapeutic Research Institute (ATRI) is for the sole use of the intended recipient(s) and contains confidential and privileged information. Any unauthorized review, use, disclosure, copying or distribution is strictly prohibited.

15 minutes after the first infusion is complete, a further 20mg/kg load of LEV will be administered IV over 15 minutes. Maintenance LEV at 10 mg/kg/dose will be given IV q8 hours and continued for at least 5 days. If seizures persist or recur more than 15 minutes after the second LEV infusion is complete, a PB loading dose of 20 mg/kg will be administered IV over 15 minutes. If seizures persist or recur more than 15 minutes after the first loading dose of PB is complete, a second 20mg/kg load will be administered IV over 15 minutes. This will result in PB being started within 1 hour of the onset of seizures if and when loading with LEV is ineffective. Patients given any PB loading doses will be started on maintenance PB with 1.5 mg/kg/dose given IV q8 hours and continued at least until the end of the study. Subjects randomized to the control group will, at the onset of electrographically confirmed seizure activity, receive an intravenous loading dose of PB of 20 mg/kg given over 15 minutes. If electrographic seizures are confirmed to persist or recur more than 15 minutes after the first infusion is complete, a further 20mg/kg load of PB will be administered IV over 15 minutes. Maintenance PB at 1.5 mg/kg/dose will be given IV q8 hours and continued for at least 5 days. If seizures persist or recur more than 15 minutes following the second PB infusion, a 40 mg/kg load of LEV will be administered IV over 15 minutes. If seizures persist or recur more than 15 minutes after the first loading dose of LEV is complete, a second 20mg/kg load of LEV will be administered IV over 15 minutes. Patients given an LEV loading doses will be started on maintenance LEV with 10 mg/kg/dose given IV q8 hours and continued at least until the end of the study.

If electrographic seizures are still apparent following treatment with both LEV and PB, or if they recur during the 5 days during which the study protocol is active, the patient will be considered to have failed the experimental treatment regime and institutional specific standard seizure management will dictate the ongoing management. Without unblinding, it will be evident that all subjects will have received 40mg/kg Phenobarbital and 60mg/kg of LEV at this stage.

*For study flow, see appendix.*

### 3.2 Specific Aims

*This section is from the NEOLEV2 Clinical Research Plan (111361 NEOLEV2 Research Plan Clean 20180413.docx)*

- Aim 1: To study the preliminary efficacy of intravenous LEV as first line treatment for neonatal seizures. The primary endpoint will be the percentage of neonates whose seizures are terminated with LEV for 48 hours, and do not go on to require a second anticonvulsant agent. A secondary endpoint will be seizure cessation for 1 hour after treatment with LEV.
- Aim 2: Dose escalation: To determine whether there is additional efficacy at higher doses of LEV than 40mg/kg. The percentage of neonates whose seizures stop following 60mg/kg LEV, having not responded to 40mg/kg LEV, will be calculated.
- Aim 3: To study the pharmacokinetics of intravenous LEV at high dosage. The hypothesis is that the pharmacokinetics of high dose intravenous LEV will follow predictions based upon previous lower dosage PK studies.
- Aim 4: To obtain further safety data regarding the use of high dose Levetiracetam in this population.
- Aim 5: **5A:** To prove the feasibility of centralized remote monitoring of continuous EEG monitoring in the NICU via the internet, thereby developing infrastructure vital to further neonatal seizure research.  
**5B:** To test the sensitivity and specificity of a promising neonatal seizure detection algorithm in comparison with readings of each record by 2 electroencephalographers skilled in neonatal EEG analysis.

**ANALYSIS OF AIMS 5A AND 5B WILL NOT BE A PART OF THE PRIMARY ANALYSIS DUE TO MONITORING CHANGES IN THE STUDY.**

### 3.3 Study Population

#### **Inclusion Criteria:**

Term newborns admitted to the UCSD, Children's Hospital and Research Center Oakland, Auckland Hospital, Rady Children's Hospital, Loma Linda University Medical Center or Sharp Mary Birch NICUs with seizures or at risk for seizures:

- Term infants (gestational age greater than or equal to 36 weeks and less than or equal to 44 weeks).
- Postnatal age < 14 days.

- Serum creatinine equal to or less than 1.6 mg/dL at time of enrollment.
- Are still experiencing either clinical or electroencephalographic seizures or are at risk for neonatal seizures.
- For whom parental consent to participate in the study is obtained.

**Exclusion criteria:**

- Biochemical abnormality - hypoglycemia, hypocalcemia - that when treated result in seizure cessation.
- Severe hypoxic ischemic injury likely to result in imminent death.
- Infants with a birth weight less than 2200 g would be excluded the study. This is the new recommended 10th percentile for 36 weeks' gestation. The blood drawn at any one time will be <3 mls/kg which remains within the NIH guidelines for pediatric blood draws.

Patients of all ethnic groups will be included in the study. Based on the patient population our group treats, most patients will be European or Hispanic. Both male and female infants will be recruited to the study.

The only significant exclusions that will be made in recruitment and enrollment will be the exclusion of infants who are judged by the attending neonatologist to be so critically ill that death is imminent and benefit from neonatal intensive care is very unlikely. No rule-based criteria, (using lab or clinical parameters) adequately capture the complete nature of this clinical assessment. In general any child receiving active treatment with head cooling will not be excluded. Mechanical ventilation and/ or the use of inotropic agents to support blood pressure will not be exclusion criteria.

### 3.4 Power and Sample Size Determination

Power calculations were based on a 2-sided chi-square test for detecting a difference between two proportions, assuming a Type 1 error of 0.05. With a sample size of 60 LEV subjects and 40 PB subject and assuming a seizure cessation rate of 50% in the control arm, we have 80% power to detect a seizure cessation rate as low as 22% (an absolute difference in seizure outcome rates of 28% or greater) in the LEV group.

### 3.5 Treatment Allocation

The two interventions are as follows:

- Group 1 (active): Levetiracetam treatment
- Group 2 (control): Standard treatment with Phenobarbital

### 3.6 Modification of Primary Aim

Aim 1 was changed from seizure termination at 48 hours after treatment to seizure termination at 24 hours after treatment. This change was approved by the FDA on September 4, 2018 (see appendix for e-mail confirmation). The updated aim 1 reads as follows:

Aim 1: To study the preliminary efficacy of intravenous LEV as first line treatment for neonatal seizures. The primary endpoint will be the percentage of neonates whose seizures are terminated with LEV for 24 hours, and do not go on to require a second anticonvulsant agent. A secondary endpoint will be seizure cessation for 48 hours and 1 hour after treatment with LEV.

## 4 Study Outcome Variables

### 4.1 Primary Outcome

- Seizure termination at 24 hours after treatment.

### 4.2 Key Secondary Outcome

- Seizure termination at 48 hours after treatment.

### 4.3 Other Secondary Outcomes

- Seizure termination at 1 hour after treatment.
- Dose escalation - Seizure termination at 24 hours following 60mg/kg LEV, having not responded to 40mg/kg.
- Length of seizure freedom.
- Phenobarbital dose

### 4.4 Safety Outcomes

- Rate of Adverse Events (AEs)
- Rate of Serious Adverse Events (SAE)
- Discontinuation Rate
- Laboratory data
- PK analysis of LEV

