40% develop cerebral palsy and/or mental retardation⁶. The most recent prospective long term follow-up of clinical neonatal seizures in the province of Newfoundland reported on all live newborns born between 1990 and 1995. Data was available on 82 of 90 children. In 28 term babies only 45% were normal, 16% died, and 32% were impaired⁶. Whilst much of the mortality and morbidity in neonates with seizures can be attributed to the underlying condition, there is mounting evidence that seizures themselves are harmful, especially in the asphyxiated neonatal brain. Studies in rats show that seizures can damage the developing brain^{7, 8}. McBride et al have demonstrated a strong correlation between the amount of electrographic seizure activity and subsequent morbidity and mortality⁹. Preliminary data also demonstrates an improved outcome with prompt and complete cessation of seizures⁴ and in a recent European controlled trial, treatment of subclinical seizures showed a trend for reduction in seizure duration which was associated with less brain injury on MRI¹⁰. Brain MR spectroscopy in neonates suffering seizures secondary to perinatal asphyxia shows brain injury as a consequence of the seizures¹¹. Recent evidence suggests that neonatal seizures independently contribute to poor outcome at 4 years of age in neonatal hypoxic-ischemic injury¹².

Current AEDs for Neonatal Seizures:

Current treatment relies on medications in use since 1914 (Phenobarbital) and 1938 (phenytoin). These agents are neither effective nor safe. Treatment with Phenobarbital or phenytoin produces cessation of neonatal seizures in less than 50% of infants treated¹. Acute side effects of phenobarbital and phenytoin include hypotension, suppression of respiratory drive, cardiac arrhythmia and sedation. Chronic exposure to phenobarbital may be associated with decreased cognitive ability¹³⁻¹⁵.

Neonatal response to AEDs is different to that of adults:

The neonatal response to AEDs is fundamentally different to that of the adult brain^{5, 16, 17}. Neonatal seizures form a unique subset of pediatric seizures for a number of reasons:

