Subjects randomised to receive LEV will, at the onset of electrographically confirmed seizure activity, receive an intravenous loading dose of LEV of 40mg/kg given over 15 minutes. If electrographic seizures are confirmed to persist or recur more than 15 minutes after the first infusion is complete, a further 20mg/kg load of LEV will be administered IV over 15 minutes. Maintenance LEV at 10 mg/kg/dose will be given IV q8 hours and continued for at least 5 days. If seizures persist or recur more than 15 minutes after the second LEV infusion is complete, a PB loading dose of 20 mg/kg will be administered IV over 15 minutes. If seizures persist or recur more than 15 minutes after the first loading dose of PB is complete, a second 20mg/kg load will be administered IV over 15 minutes. This will result in PB being started within 1 hour of the onset of seizures if and when loading with LEV is ineffective. Patients given any PB loading doses will be started on maintenance PB with 1.5 mg/kg/dose given IV q8 hours and continued at least until the end of the study

Figure 2 details the study flow.

Subjects randomized to the control group will, at the onset of electrographically confirmed seizure activity, receive an intravenous loading dose of PB of 20 mg/kg given over 15 minutes. If electrographic seizures are confirmed to persist or recur more than 15 minutes after the first infusion is complete, a further 20mg/kg load of PB will be administered IV over 15 minutes. Maintenance PB at 1.5 mg/kg/dose will be given IV q8 hours and continued for at least 5 days. If seizures persist or recur more than 15 minutes following the second PB infusion, a 40 mg/kg load of LEV will be administered IV over 15 minutes. If seizures persist or recur more than 15 minutes after the first loading dose of LEV is complete, a second 20mg/kg load of LEV will be administered IV over 15 minutes. Patients given an LEV loading doses will be started on maintenance LEV with 10 mg/kg/dose given IV q8 hours and continued at least until the end of the study.

If electrographic seizures are still apparent following treatment with both LEV and PB, or if they recur during the 5 days during which the study protocol is active, the patient will be considered to have failed the experimental treatment regime and institutional specific standard seizure management will dictate the ongoing

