Feasibility data: We will record the times of the following events: subject admission to NICU, contact of study staff by treating physicians, subject enrolment, initiation of EEG monitoring, first recognized seizure, and time of study drug administration. Record will be made of whether seizure is first identified by Corticare staff or by onsite study investigator. Record will be systematically collected from each monitored subject of any difficulties with functioning of the remote continuous monitoring infrastructure. All data will be referenced to date/time of birth so that precise age in hours can be determined for age at enrolment, timing of seizures, administration of study drug, and administration of other treatments given to treat seizures.

Safety data: Continuous monitoring of vital signs will occur as part of routine neonatal intensive care. Vital signs will be recorded at baseline, and at 15 minutes after each drug infusion commences. Documentation of presence or absence of adverse event occurring during each treatment phase will be made. Blood tests of haematological indices, electrolytes, glucose, renal function and liver enzymes will be tested and recorded at baseline, at 24 hours and at 48 hours as part of safety and adverse events monitoring.

Pharmacokinetic data: For subjects at the 3 San Diego sites serum LEV levels will be drawn at baseline, 1 hour after starting the treatment, at 24 and 48 hours.

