The actual individual concentration data, collection times and dosing histories will be used to create graphs of plasma LEV concentration vs. time for each infant. Median plasma drug concentration vs. time curves will also be generated. Summary statistics (i.e., n, mean, standard deviation, median, minimum, maximum, and coefficient of variation) will be calculated for plasma concentrations for each time point and each dose level. LEV population pharmacokinetic parameters will be determined using the computer program NONMEM (ver. 6 or later). The data will be nested with existing raw infant LEV pharmacokinetic data generated in the preliminary LEV study. Assuming linear pharmacokinetics as suggested by our current pharmacokinetic data, studying 12 subjects at each dosage level will result in 90% confidence intervals for the pharmacokinetic parameters (CL, V and $t_{1/2}$) of +/- 15%. The 90% confidence intervals for the exposure parameters (C_{max} , AUC) will be approximately +/- 20%. The pharmacokinetics will be modeled recognizing the two stages of a nonlinear hierarchical model development. The first stage introduces the structural model (e.g. one compartment open model), the population parameters, individual effects and the within-patient variation. The second portion of the model development recognizes that variation between patients in the pharmacokinetic parameters exists and will attempt to determine covariates that may identify different pharmacokinetic subpopulations. A one-compartment model with first order elimination will be utilized. Alternative structural models will be explored if indicated by the data. The impact of clinical factors and demographic factors (including weight, sex, age, race, serum creatinine, hypothermia and dosing regimen) will be assessed as fixed effects in the model. Nested models will be compared graphically and with a likelihood ratio test.

Analysis Plan for Aim 4: Safety analysis

A Fisher's exact test will be used to compare rates of adverse events, serious adverse events and study discontinuation rates between the LEV and control groups.

Analysis Plan for Aim 5 A: Feasibility of remote continuous EEG monitoring system

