## 7.5 Analysis of Safety Outcomes

Adverse Event and Serious Adverse Events will be tabulated by randomization group and by drugs received, respectively. Details including seriousness, intensity, causality, withdrawal due to event and outcome will be summarized by frequencies and percentages by randomization group and by drugs received. Fisher's exact tests will be used to compare rates of adverse events, serious adverse events, study discontinuation and deaths between randomization group and by drugs received, respectively.

Findings will be tabulated by randomization group overall and for findings marked as AE and SAE, respectively.

Safety Labs (using DAIDS guidelines) will be presented with shift tables (hour 48 vs baseline) by randomization group and by drugs received, respectively.

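### Safety is compared only over the whole trial or by drugs received; a randomised comparison limited to the first load, including the scheduled vital signs, should be added

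*SAP*

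**What the plan says.** **What is collected.** Protocol section 8, Data to be collected (Safety data): "Vital signs will be recorded at baseline, and at 15 minutes after each drug infusion commences". The same paragraph adds: "Documentation of presence or absence of adverse event occurring during each treatment phase will be made".

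**What is analysed.** The protocol's Analysis Plan for Aim 4 uses Fisher's exact test to "compare rates of adverse events, serious adverse events and study discontinuation rates between the LEV and control groups". SAP 4.4 lists adverse events (AEs), "Rate of Serious Adverse Events (SAE", discontinuation, laboratory data and LEV pharmacokinetics. SAP 7.5 uses Fisher's exact tests to "compare rates of adverse events, serious adverse events, study discontinuation and deaths between randomization group and by drugs received". It adds laboratory shift tables at hour 48 and one further line: "Findings will be tabulated by randomization group overall and for findings marked as AE and SAE, respectively". The term 'Findings' is not defined, and no test is attached to it.

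**How the drugs mix.** Protocol section 8, Study Design Summary, for the LEV arm: "If seizures persist or recur more than 15 minutes after the second LEV infusion is complete, a PB loading dose of 20 mg/kg" is given. The PB arm mirrors this, with LEV after two failed PB loads. Infants who fail the full sequence have had both drugs at the same total loads, whichever arm they were in.

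**The concern.** The protocol's Plan for Statistical Analysis says that the LEV and PB groups will be compared on safety, and safety of high-dose LEV is Specific Aim 4. The known hazards of the control treatment are acute. Protocol section 6 states: "Acute side effects of phenobarbital and phenytoin include hypotension, suppression of respiratory drive, cardiac arrhythmia and sedation". Such effects would be expected during or soon after a load.

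Neither planned contrast isolates them with randomisation intact. Over the whole trial, part of the LEV arm has also been loaded with PB, so a PB effect appears in both arms. When infants are grouped by drugs received, those given both drugs are by design the ones who did not respond, so severity of illness is mixed with exposure. The first two loads in each arm are the assigned drug alone, so a cleaner contrast is available. The plan does not name it, and it names no analysis of the scheduled vital signs.

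At stake is how well the trial can describe acute drug safety for a phase III decision.

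**Working it through.** The plan states no figure on this point, so there is none to reproduce. The omission is checked from the text, and its size is illustrated under stated assumptions.

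**1. The texts side by side**

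| Place | Content | Vital signs named? | Time window? |
|---|---|---|---|
| Protocol 8, Safety data | Vital signs at each infusion; AEs by treatment phase | Yes | Yes (collection) |
| Protocol 8, Aim 4 analysis | AEs, serious AEs, discontinuation by arm | No | No |
| SAP 4.4 | AEs, serious AEs, discontinuation, laboratory, PK | No | No |
| SAP 7.5 | The above plus deaths and 'Findings', by arm or drugs received | No | Only laboratory (hour 48) |

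**2. When the opposite drug can first be given.** First load 15 min + wait 15 + second load 15 + wait 15 = 60 minutes after the first load starts. The vital signs taken at 15 minutes of the first infusion therefore precede crossover in every treated infant.

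**3. Dilution over the whole trial.** Let b be the base AE rate, e the excess caused by PB and R the LEV response rate, and assume LEV adds no risk.
- PB arm: b + e. LEV arm: b + e(1 − R). Difference: eR, so the share kept is R.
- The documents give no AE rates. Assume b = 10% and e = 20 points, with the planned 60 LEV and 40 PB infants.

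| R | LEV vs PB | Difference | Exact Fisher power (two-sided 0.05) |
|---|---|---|---|
| 22% | 25.6% vs 30% | 4.4 points | 6% |
| 50% | 20% vs 30% | 10 points | 18% |
| 60% | 18% vs 30% | 12 points | 25% |

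The 50% is the control cessation rate in SAP 3.4, borrowed here for LEV. The 22% is the detectable alternative in the same section, not an expected rate.

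**4. Comparison before crossover.** Let f be the fraction of both base and excess events that fall in the window. The rates are f·b for LEV and f·(b + e) for PB.

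| f | LEV vs PB | Exact Fisher power |
|---|---|---|
| 1 | 10% vs 30% | 67% |
| 1/2 | 5% vs 15% | 32% |
| 1/4 | 2.5% vs 7.5% | 14.5% |

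At f = 1 the Newcombe 95% CI for the difference is 4 to 36 points. For the whole trial at R = 50% it is −7 to 28 points. At f = 1/4 power is below the whole-trial 18%. The documents do not give f.

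**5. Precision for a vital sign, 60 vs 40.**
- Unadjusted 95% CI half-width: t(0.975, 98) × √(1/60 + 1/40) = 1.984 × 0.2041 = 0.405 SD.
- Adjusted for baseline with assumed correlation 0.5: t(0.975, 97) × √(0.75 × (1/60 + 1/40)) = 0.351 SD.
- Unadjusted t-test power for true differences of 0.2, 0.4 and 0.6 SD: 16%, 49% and 83%.

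**The case against.** The strongest reply has five parts.

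- **The investigators anticipated crossover.** SAP 7.5 reports by drugs received as well as by arm, and hypotension or apnoea reported as an AE enters those tables. This is true. But those tables remain either diluted or grouped by response, and the scheduled readings themselves go unanalysed unless 'Findings' covers them, which the SAP does not say.
- **Treatment strategy is the right question for a first-line drug.** This stands. A reader might infer that the whole-trial comparison by arm is invalid. The documents do not support that: it is a sound randomised comparison of LEV-first with PB-first care, and the proposal adds to it.
- **The power gain is uncertain.** This stands. A reader might take 67% against 18% as the benefit. That contrast needs every base and excess event to occur before crossover, which can be as early as 60 minutes, while treatment runs at least 5 days.
- **Phases depend on response.** This stands. Further loads are triggered when seizures persist or recur, with no stated upper time limit, so the window through the second load can differ in length between arms. The first-load phase shares this weakness unless its end is fixed. The 15-minute reading does not.
- **Some data are unconfirmed.** The protocol does not say which vital signs are recorded at 15 minutes, whether AE onset times are kept, or whether ventilation status is collected with them. The fix should therefore not depend on a ventilation-restricted analysis, and the 60-minute window must be conditional.

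Exploratory analyses are allowed under SAP section 1, but they must be labelled unplanned. Naming this one in advance avoids choosing the window after seeing results.

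**Conclusion.** The concern holds as a worthwhile, low-cost addition. The safety plan has no randomised comparison confined to the period before crossover and names no analysis of the scheduled vital signs. Its two contrasts are a valid but diluted one and one confounded by response.

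The dilution has a simple size: if LEV adds no risk, the whole-trial difference keeps a fraction of any PB excess equal to the LEV response rate. The gain from a first-load comparison is an unmixed randomised estimate with its interval. Whether it also gains power depends on the timing of events: 67%, 32% or 14.5% against 18%, all under assumed rates.

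Two further inferences would go too far. The documents do not show that vital signs go uncollected, since the protocol schedules them. Nor does anything here touch the efficacy analyses: no primary or key secondary conclusion changes.

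**What to change.** In SAP 4.4 and 7.5, for all infants given a first load, add:

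1. **Vital signs.** Compare the randomised arms on the vital signs recorded at 15 minutes of the first infusion, adjusted for baseline. Report the difference, 95% CI and number with paired readings.
2. **First-load AEs.** Compare by randomised arm the proportion with an AE in the first-load phase, with difference and 95% CI. Keep every first-loaded infant in the denominator.
3. **Supportive windows.** Report the period through the second load, before any opposite drug, as supportive only. If AE onset times exist, use a fixed 60-minute window from the start of the first load.
4. **Later infusions.** Summarise descriptively by drug and load number.
5. **Definitions.** Define 'treatment phase', including when the first-load phase ends, and state whether 'Findings' includes vital signs.

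Keep the planned comparisons by arm and by drugs received.

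**Cost.** SAP wording, two tables and one simple model per vital sign; items 1 and 2 use data the protocol already schedules. The downsides are a few extra safety comparisons, modestly powered and not adjusted for multiplicity, and reliance on a single end-of-infusion reading that can miss later effects.
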